10.2 Follow-up scans

Evolution of lesions over the period of time provides invaluable help in the verification of original interpretation of the scans even in the absence of biopsy. Therefore all the patients will undergo follow up scans (the type advised by radiologist) 4-6 months after registration to the protocol. These scans will be interpreted in the context of ongoing therapy (i.e. hormonal therapy) or observation. Several possible scenarios will allow us to interpret and verify the findings on the original scans.

- a) The persistence, growth, increase in numbers and intensity of enhancement of lesions in patients on observation would strongly favor the interpretation of a true positive finding.
- b) Complete stability over time or resolution of lesions without ongoing therapy would strongly favor false positive interpretation.
- c) Evolution of lesions (regression, radiologic signs of healing in the context of ongoing hormonal therapy (and lack of any history of trauma) would strongly support the interpretation of true positive scans
- d) Complete stability of lesions despite ongoing hormonal therapy would favor false positive interpretation

By combining these three elements of verification of original interpretation of WB/axial MRI and F-18 NaF PET/CT we will be able to provide the most robust assessment of sensitivity and specificity of these imaging modalities in the literature that may prove to be quite useful in the management of patients with biochemically recurrent prostate cancer.

Table 1

Interpretation of Imaging with WB/axial MRI and F-18 NaF PET/CT based on subsequent biopsy, therapy and follow up imaging (not all patients will be classified as below depending on additional systemic therapy given)

Original MRI/PET Interpretation	Biopsy	PSA response to salvage RT	Follow up scans	FINAL Interpretation of Baseline MRI/PET	
Mets	+	NA	Regardless	TP	
			Mets	Indeterminate	
			Indeterminate	FP	
			No mets	FP	
		≥ 0.04	Mets	TP	
	- or NA		Indeterminate	TP	
			No mets	Indeterminate	
	NA	Mets	TP		
		Indeterminate	TP		
		No mets	FP		
Indeterminate	+	NA	Regardless	TP	
			Mets	Indeterminate	
			Indeterminate	FP	
		≥ 0.04	No mets	FP	
			Mets	TP	
	- or NA	≥ 0.04	Indeterminate	TP	
			No mets	Indeterminate	
		NA	Mets	TP	
			Indeterminate	Indeterminate	
			No mets	FP	
Negative	N/A	<0.04	Mets	Indeterminate	
			Indeterminate	TN	
			No mets	TN	
		≥ 0.04	Mets	FN	
			Indeterminate	FN	
			No mets	Indeterminate	
		NA	Mets	Indeterminate	
			Indeterminate	TN	
			No mets	TN	

TN – True negative

FN – False negative

TP – True positive

FP – False positive

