Patients who were classified as having negative bone scan and CT scan (estimated $\geq 90\%$ of patients) will undergo MRI (axial MRI and WB MRI) and F-18 NaF PET/CT. The outcome of these studies will be reported as 1) consistent with visible recurrence, 2) indeterminate 3) negative. In cases of findings consistent with visible recurrence or indeterminate a biopsy of the lesion of interest will be recommended if feasible. Any enrolled patient without a positive biopsy will be followed and their treatment (at discretion of treating physician), PSA values and outcome will be recorded to evaluate the scan result specificity and sensitivity in relation to additional information provided with follow-up (e.g. if patients undergo Salvage Radiation Therapy, PSA response will be recorded which will have significant implication in the interpretation of radiologic findings (see 10). Subsequently all patients without biopsy proven metastasis will undergo follow up imaging studies (the type of imaging to be recommended by radiologist)) within 4-6 months to reassess any abnormalities in the context of time, ongoing therapy or no therapy.

Sample Size:

Total Sample size is 56. Anticipated accrual is 2-3 patients a month.

Estimated Duration of the Study

24 months

Summary of Subject Eligibility Criteria:

Patients with 2 PSA values ≥ 0.2 ng/mL at least 4 weeks after surgery will be evaluated. Patients who were started on androgen deprivation therapy will not be allowed on this protocol. Patients who have started radiographic evaluation and underwent CT scan and/ or BS prior to registration to the study will be able to participate under a late registration provision, provided that WB/axial MRI and F-18 NaF PET/CT can be completed within 4 weeks of the CT scan and BS.

Investigational Product Dosage and Administration:

Not Applicable.

Clinical Observations and Tests to be Performed:

CT of the chest, abdomen and pelvis and bone scan. Targeted X Rays if suggested by the radiologist. If negative, WB/axial MRI and F-18 Sodium Fluoride PET /CT. Biopsy of suspected lesions will be performed if feasible, and repeat scans will be performed for patients with suspicious lesions.

Statistical Considerations:

Sponsor/Licensee:

City of Hope

Case Report Forms

Table of Contents

SECTION	PAGE
1.0 Objectives	8
2.0 Background.....	9
2.1 Introduction/Rationale for Development	9
2.2 Overview of Proposed Study	11
3.0 Patient Eligibility	12
3.1 Inclusion Criteria	12

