Currently at City of Hope, patients who present with a PSA level of ≥ 0.2 ng/mL after radical prostatectomy typically undergo computed tomography scan (CT) of the abdomen and pelvis, bone scan (BS), targeted X-rays (TXR), and occasionally Prostascint scanning, with the primary goal of excluding the presence of metastatic disease. However, these imaging modalities often fail to detect metastatic disease, especially early in the course of PC recurrence when the cancer burden is low.⁵ The value of abdominal and pelvic CT in the detection of metastases in patients with biochemically-recurrent PC is low, especially when PSA levels are < 10 ng/mL.⁶ The detection of metastatic bone cancer with BS is low because it detects bone deposits from osteoblasts, not directly from cancer cells.⁷ BS is positive in $< 1\%$ of patients who present with biochemically-recurrent PC and a PSA level of < 10 ng/mL.⁵ Prostascint scanning has significant limitations because it only recognizes the intracellular domain of prostate specific membrane antigen (PSMA) and, likely due to the low detection rate, Prostascint scans do not correlate with the efficacy of salvage RT in PC.⁸ As a result, the reported long-term success rate of salvage RT (in patients with negative CT scan and bone scan) ranges from 10-50%. This suggests that the majority of patients (50-90%) with biochemically-recurrent PC have occult metastases that are not visualized by standard imaging approaches,^{9,10,11} It is therefore clinically very important to improve the accuracy of radiologic assessment of patients with biochemically recurrent PC. This may have significant importance in the appropriate selection of patients for local salvage therapy or systemic treatments. Our

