3. To correlate the presence of metastatic disease detected using WB/axial MRI and/or F-18 NaF PET/CT with the predicted 6-year probability of progression-free survival based on the Memorial Sloan Kettering Cancer Center salvage RT PC nomogram, and with PSA level at baseline.
4. To compare the role of axial MRI of the spine to WB MRI with respect to their ability to identify sites of disease. Similarly, to evaluate the relative contribution of F-18 NaF PET and MRI. This is an exploratory aim as the number of patients with sites of disease visualized on the MRI technology will not be known a priori.

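### Follow-up verification is not tied to the site of the baseline lesion, so a new metastasis elsewhere can upgrade the final call on the baseline MRI/PET

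*Combined protocol and SAP*

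**What the plan says.** The synopsis says the repeat imaging is there "to reassess any abnormalities in the context of time, ongoing therapy or no therapy". The Follow-up scans section (10.2) says: "Therefore all the patients will undergo follow up scans (the type advised by radiologist) 4-6 months after registration to the protocol". The repeat modality may therefore differ from the baseline one.

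That section gives four scenarios for interpreting the repeat scan. Two matter here:
- Scenario (a): "The persistence, growth, increase in numbers and intensity of enhancement of lesions in patients on observation would strongly favor" a true-positive interpretation.
- Scenario (b): "Complete stability over time or resolution of lesions without ongoing therapy would strongly favor false positive interpretation".

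Table 1 of the same section then fixes the result. It classifies men, with the caveat that "not all patients will be classified as below depending on additional systemic therapy given", and its output column is headed "FINAL Interpretation of Baseline MRI/PET". The inputs are the baseline read, biopsy, PSA after salvage RT, and one follow-up code. There is no column for site, and nothing in the section requires a follow-up metastasis to be the lesion seen at baseline. Negative biopsy and no biopsy share one category.

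The section presents the combined verification as the basis for estimating sensitivity and specificity. Section 12.0 adds that follow-up scans and treatment results will feed the final judgement of success, without a numerical rule.

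**The concern.** The purpose of verification is to learn whether what the new scans showed was real. A follow-up code that asks only whether the man now has metastases answers a different question. A benign lesion at baseline can be confirmed by disease that appears somewhere else.

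The plan's own premise makes this foreseeable. Section 2.1 infers that the "majority of patients (50-90%) with biochemically-recurrent PC have occult metastases that are not visualized by standard imaging approaches". Some of that disease may become visible by 4-6 months whether or not the baseline lesion was real. Section 10.1.1 expects biopsy in only about 25% of cases with suspicious lesions, which leaves about 100% − 25% = 75% to be verified by PSA response and repeat scans. At stake is the credibility of the sensitivity and specificity that the study promises.

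**Working it through.** **1. The plan's own figure.** Section 12.0 requires at least 4 positives among 45 men and states a type I error below 5% at a 3% rate and power above 86% at a 15% rate. Exact binomial: P(X ≥ 4 | n = 45, p = 0.03) = 0.0456 and P(X ≥ 4 | n = 45, p = 0.15) = 0.9215. Both stated bounds hold and are not in dispute. This count is of reads on the newer scans, before verification.

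**2. Table 1 read row by row, biopsy negative or not done.** The first PSA label is missing from the extracted text for the Mets and Indeterminate reads. It is taken as <0.04 by comparison with the Negative block, and the row alignment in the Indeterminate block is read the same way. NA means no salvage RT result.

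| Baseline read | PSA after salvage RT | Follow-up No mets | Follow-up Indeterminate | Follow-up Mets |
|---|---|---|---|---|
| Mets | <0.04 (inferred) | FP | FP | Indeterminate |
| Mets | ≥0.04 | Indeterminate | TP | TP |
| Mets | NA | FP | TP | TP |
| Indeterminate | <0.04 (inferred) | FP | FP | Indeterminate |
| Indeterminate | ≥0.04 | Indeterminate | TP | TP |
| Indeterminate | NA | FP | Indeterminate | TP |
| Negative | <0.04 | TN | TN | Indeterminate |
| Negative | ≥0.04 | Indeterminate | FN | FN |
| Negative | NA | TN | TN | Indeterminate |

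**3. The shift caused by an unrelated new lesion.** Suppose the baseline site alone would be coded No mets, and a new metastasis elsewhere makes the man's code Mets. Moving from the third column to the last, for a baseline read of Mets or Indeterminate:
- no salvage RT: FP becomes TP;
- PSA ≥0.04: Indeterminate becomes TP;
- PSA <0.04: FP becomes Indeterminate.

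A man whose baseline lesion was biopsied and found negative follows the same path.

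**4. Scenarios (a) and (b) side by side.** Take a man on observation whose baseline lesion is completely stable and who has one new metastasis. The number of lesions has risen, so (a) points to TP. The baseline lesion is stable without therapy, so (b) points to FP. The text gives no order of precedence, and the no-RT row of Table 1 settles the case as TP.

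**5. Direction.** Write sensitivity = TP/(TP + FN), specificity = TN/(TN + FP), PPV = TP/(TP + FP), with Indeterminate calls left out (an assumption; the plan does not say how they are handled).
- FP to TP raises all three, given that each is below 100% beforehand and its numerator is not zero.
- Indeterminate to TP raises sensitivity and PPV, on the same proviso.
- FP to Indeterminate raises specificity and PPV, on the same proviso.

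There is also an asymmetry: without salvage RT, a metastasis at follow-up scores TP after a positive or indeterminate baseline read, but only Indeterminate, not FN, after a negative one.

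**6. Size.** The documents give no rate at which such men occur. What can be computed is the effect of one man. With k baseline-positive men, all classified TP or FP, PPV = TP/k, so one man moved from FP to TP changes it by 1/k. The plan's threshold gives k = 4; its 15% rate gives 0.15 × 45 = 6.75, about 7. Hence 1/4 = 25 points and 1/7 = 14 points.

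**The case against.** The strongest reply is that the question is per patient. The primary objective is a proportion of men, and the intended use is to identify men with distant disease. A man with a metastasis at 4-6 months may well have had it at baseline, so a positive scan in him is a patient-level true positive. The man is indeed the right unit and should stay so. But the plan does not hold to that reference standard. The PSA-response scenarios treat visible lesions outside the radiation field as false positives when PSA becomes undetectable, and name benign visible lesions with disease elsewhere as the competing explanation to a true positive. A consistent patient-level standard would also score a negative baseline scan followed by metastases as FN; without salvage RT, Table 1 scores it Indeterminate.

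Second, the text shows lesion-level intent: follow-up is meant to reassess abnormalities, scenario (b) concerns the fate of the lesion, and scenario (a) is limited to men on observation and only says what would be favoured. That stands. The fixed TP comes from Table 1, which does not carry the intent through.

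Third, outright conversion from FP to TP is confined to the no-RT row, and the plan expects most men without biopsy-proven metastases to be offered salvage RT. This limits the point. How many baseline-positive men fall in that row is not stated; section 2.1 hopes to spare men with detected metastases that treatment.

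Some stronger readings do not hold:
- A reader might infer that one positive biopsy wrongly validates a multi-lesion scan. With the man as the unit, one proven baseline lesion is enough.
- A reader might infer that the fourth secondary objective, which compares modalities "with respect to their ability to identify sites of disease", is undermined. It is exploratory, and nothing ties it to Table 1.

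**Conclusion.** The point holds in a limited form. As written, the verification rule can upgrade the final call on a baseline scan because of a metastasis at another site, and scenarios (a) and (b) can conflict without a stated precedence. All three shifts favour the new scans, in the accuracy estimates and potentially in the final judgement of success. It should be corrected, but it does not invalidate the design.

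The overall size is unknown. A reader might infer it by multiplying the 50-90% occult-disease figure by some rate of new visibility. The documents give no such rate, the 50-90% is not specific to men with a benign MRI/PET lesion, and the product would ignore the PSA rows. The supportable figure is the conditional one: 14 to 25 points of PPV per man rescored from FP to TP, assuming 4 to 7 baseline-positive men who are all classified TP or FP. PPV is used here as a convenient measure; the plan itself speaks of sensitivity and specificity.

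A reader might also infer that the type I error of the 4-of-45 rule is inflated. The documents do not support that: the count rests on baseline reads, and verification enters only through a judgement with no numerical criterion. The <0.04 row depends on an inferred label.

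**What to change.** - Record the anatomical site of every baseline MRI/PET lesion read as metastatic or indeterminate.
- Code Table 1's follow-up column for that same site.
- Keep the man as the unit: call him TP if at least one baseline lesion is confirmed at its own site.
- Record new lesions elsewhere separately, and state that they cannot alone confirm a baseline lesion. A rise in lesion number may still be reported as evidence of progression.
- State that the site-matched result prevails when scenarios (a) and (b) conflict.

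The cost is a short lesion log on the case report form, a line added to Table 1, and slightly more Indeterminate results, chiefly where the repeat modality cannot show the baseline site. The sample size and the 4-of-45 rule need no change on this account.

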11.0 Data Reporting/Protocol Deviations

11.1 Confidentiality and Storage of Records

The original data collection forms will be stored at the originating institution in a secure location. Study data will be entered into an electronic case report form (eCRF) using an encrypted, password protected, secure electronic data capture (EDC) application that meets all HIPAA requirements. When results of this study are reported in medical journals or at meetings, identification of those taking part will not be disclosed. Medical records of subjects will be securely maintained in the strictest confidence, according to current legal requirements. They will be made available for review, as required by the FDA, HHS, or other authorized users such as the NCI, under the guidelines established by the Federal Privacy Act and rules for the protection of human subjects.

11.2 Subject Consent Form

The original signed and dated Informed Consent form, HIPAA research authorization form, and the California Experimental Subject's Bill of Rights will be stored in the research record. At the time of registration, a copy of the original signed and dated consent documents will be available to the patient and another copy will be stored in the medical record. All Institutional, NCI, Federal, and State of California requirements will be fulfilled.

11.3 Data Collection Forms and Submission Schedule

All data will be collected using Medidata EDC electronic case report forms. Data will be sent to the City of Hope Department of Biostatistics and stored in a secure location.

11.3.1 Eligibility Checklist

The Eligibility Checklist must be completed by a protocol nurse or clinical research associate and signed by an authorized investigator prior to registering the subject. See Section 4.3 for the registration procedure.

11.3.2 Prior Therapy Forms and On-Study Forms

Within two weeks of registration, the clinical research associate will submit Prior Therapy Forms and On-Study Forms.

11.4 Protocol Deviations

11.4.1 Deviation Policy

This protocol will be conducted in accordance with COH's "Clinical Research Protocol Deviation Policy" located at <http://www.coh.org/dsmc/Documents/Institutional%20Deviation%20Policy.pdf>.

Deviations from the written protocol that could increase patient risk or alter protocol integrity require prior IRB approval of a single subject exception (SSE) request. In addition, if contractually obligated, the sponsor must also approve the deviation. IRB pre-approved SSE protocol modifications are considered an amendment to the protocol and not a deviation. The submission of a deviation report is not required.

Brief interruptions and delays may occasionally be required due to travel delays, airport closure, inclement weather, family responsibilities, security alerts, government holidays, etc. This can also extend to complications of disease or unrelated medical illnesses not related to disease progression. The PI has the discretion to deviate from the protocol when necessary so long as such deviation does not threaten patient safety or protocol scientific integrity. Examples include, but are not limited to: a) dose adjustments based on excessive patient weight; b) alteration in

treatment schedule due to non-availability of the research participant for treatment; c) laboratory test results which are slightly outside the protocol requirements but at levels that do not affect participant safety. These instances are considered to be deviations from the protocol. A deviation report will be submitted to the DSMC/IRB within five days.

11.4.2 Reporting of Deviations

All deviations will be reported to the COH DSMC within five days. The DSMC will forward to report to the IRB following review.

11.4.3 Resolving Disputes

The COH Investigational Drug Service (IDS) cannot release a research agent that would cause a protocol deviation without approval by the PI. Whenever the protocol is ambiguous on a key point, the IDS should rely on the PI to clarify the issue.

In situations where there is misperception or dispute regarding a protocol deviation among the persons involved in implementing the protocol, it is the responsibility of the PI to resolve the dispute and the PI may consult with the DSMC chair (or designee) to arrive at resolution.

12.0 Statistical Considerations

We expect more than 90% of the patients enrolling in this study will be negative for metastatic disease based on CT, bone scan and targeted X-rays if ordered.

Primary Endpoint/Sample size justification:

With 56 patients enrolled, we expect more than 45 patients or more to be negative for metastatic disease based on CT, bone scan and X-rays. Historically, more than half of these patients are expected to have undocumented metastatic disease. The use of WB/axial MRI and 18-F NaF PET will be considered worthwhile if more than 8% of these patients (8% rate) are determined to be positive for metastatic disease based on the newer scan technologies. Assuming 45 patients, this requires at least 4 patients to be determined to have metastatic disease on the newer scans that were considered to be without metastatic disease on the standard scans. With 45 patients, and requiring at least 4 patients, there is less than a 5% chance of declaring a discouraging 3% rate to be promising (type I error), and greater than 86% power for declaring a true 15% rate to be a success. The actual power should be higher as it is expected number of patients negative on standard scans is approximately 49 patients. The percent of patients with negative standard scans and positive on the newer scans can be estimated with a 95% CI half-width of less than 15%. Final determination of success will include an evaluation of the follow-up scans and treatment results (when applicable) to fully evaluate the role of the newer scans.

Accrual:

56 patients will be accrued over 24 months for an accrual rate between 2-3 patients a month.

Secondary Endpoints:

The secondary endpoints in the context of this study are exploratory:

1. To estimate the percent of eligible patients with negative, indeterminate and positive CT scan/bone scan and targeted X-rays if done. With 56 patients, the percent positive for metastatic disease can be estimated with a 95% CI half-width of less than 13%.

2. To determine the proportion of patients with biochemically recurrent PC in whom recurrence in the prostate bed can be visualized using MRI in the absence of detection using CT scan. This is exploratory, since detection in the prostate bed on CT does not preclude patients from RT salvage therapy, the denominator for this rate will not be known or estimated a priori.
3. To correlate the presence of metastatic disease detected using WB/axial MRI and/or F-18 NaF PET/CT with the predicted 6-year probability of progression-free survival based on the Memorial Sloan Kettering Cancer Center salvage RT PC nomogram, and with PSA level at baseline.
4. To compare the role of axial MRI of the spine to WB MRI with respect to their ability to identify sites of disease. Similarly, to evaluate the relative contribution of F-18 NaF PET and MRI. This is an exploratory aim as the number of patients with sites of disease visualized on the MRI technology will not be known a priori.

